Latin American Registry of Cardiogenic Shock in the context of Acute Coronary Syndromes (LATIN-Shock)

Investigation area Argentine Society of Cardiology

Index

Introduction	3
Objetives	3
Methods	3
Study design	
Inclusion criteria	
Exclusion criteria	
Information gathering	
Statistic analysis	
Ethical considerations	
Study organization	
Publications	
Bibliography	

Introduction:

Cardiogenic shock is a rare disease, but it constitutes the main cause of mortality in patients hospitalized for acute myocardial infarction. Its incidence ranges between 7 and 10% of infarction cases ¹ and it is associated with a mortality of 40-50% despite revascularization and the use of intra-Aortic Balloon Contrapulsation ²⁻³⁻⁴.

Most of the bibliography on this topic is North American, it is already many years old ⁵⁻⁶ and the one that is currently published mainly shows the results of different ventricular supports that are not commonly used in our environment ⁷. So far there is no record that reports the reality of Latin America. Only in Argentina, has carried out a national registry of cardiogenic shock in the context of acute coronary syndromes but have already spent more than 5 years since its publication⁸. In recent years have even changed management guidelines this pathology ⁹⁻¹⁰ and works have been published that could have changed previous behaviors ¹¹.

This is a project of the Argentine Society of Cardiology to collect epidemiological data and current management of cardiogenic shock in Latin America.

Objetives:

- 1- Determine the clinical characteristics of patients who are admitted to the coronary unit with acute coronary symptoms and present Cardiogenic Shock, either from admission or during their in-hospital evolution.
- 2- Analyze the treatment of patients with cardiogenic shock.
- 3- Observe the clinical in-hospital evolution.
- 4- Evaluates predictors of in-hospital mortality.
- 5- Compare the clinic, management and evolution characteristics in the different participating Latin American countries.

Methods:

Study design:

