As it is a study that involves different countries, the data will be analyzed globally and by country initially. Different sub-studies may be carried out with the information obtained. Each participating country has the right to submit ideas for conducting sub-studies. In that case, they must be formally presented to the Executive Committee, who will carry out the analysis and provide the data if the proposal is accepted. The sub-studies should be re-evaluated by the ethics committee.

Each participating Scientific Society will receive an Excel with the data of their country once the study is finished (anonymized data) that they can present at conferences or for publication as national experiences. Each participating center

will have available immediately statistical reports (automatically generated) of the patients who have entered their center.

File in Red Cap: http://redcap.sac.org.ar/redcap/surveys/?s=RMCAYAXMF3

Statistic analysis:

The information obtained will be incorporated into a database that will be analyzed using the statistical programs Epi-info and / or IBM SPSS. For each of the observed variables, a frequency table will be constructed.

Continuous variables will be expressed as mean and standard deviation for those with a normal or Gaussian distribution and as a median with an interquartile range 25% -75% for those without such distribution. The comparison between these variables will be carried out using the Student's t test or the Wilcoxon ranksum test, as appropriate.

Discrete variables will be expressed as percentages. Statistical comparisons between them will be made using the chi-square test with Yates correction or Fisher's exact test, as appropriate.

Contingency tables will be constructed to analyze the association or independence of the variables. The analysis of the existence of associations and / or independent predictions between the different variables involved and the end points will be carried out by means of linear regression analysis and / or multiple logistic. The variables of univariate statistical significance will be entered for evaluation in the different regression models. The value corresponding to each covariate of the aforementioned analysis will be expressed as adjusted Odds Ratio and its corresponding 95% confidence interval. All statistical comparisons will be two-tailed, and p values <0.05 will be considered statistically significant.

Consent of the patient

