LATIN-Shock, as an observational study, only requires data that has already been collected and is available in the patient's medical record. It does not require sensitive data. It does not involve specific interventions and there is no follow-up after discharge, therefore, informed consent is not required. However, this could be adjusted according to local regulations of the participating countries.

Ethical considerations

The protocol and the registration form will be submitted for approval by the ethics committee of the Sociedad Argentina de Cardiología, [name]. The study will be carried out in accordance with national and international ethical standards (CABA Law No. 3301, Declaration of Helsinki, and others).

As it is a descriptive study in which the data will be those normally collected in this pathology and there will be no identification of the patient or out-of-hospital follow-up, the signing of informed consent will not be required.

Study organization:

Executive committee:

Directors: [name] - [name]

Scientific and organizational secretariat: It is responsible for the organization of research, control, management and preparation of data analysis reports. It will be made up of: [name], [name], [name].

Each participating Latin American Society of Cardiology will be represented by one / two members (designated by its president) and they will be the ones who appear in the final document and receive the database of their country at the end of the study.

Collaborators: This is the name given to the members of the centers where the inclusion of the participants takes place. The head of each center where the investigation is carried out and another doctor designated by him will be specially invited, who will be in charge of preparing the registration forms.

Participating Centers:

Other Spanish-speaking Latin American Cardiology Societies will be invited to participate and they will designate the coronary units where the registry will be carried out.

Sample: It is estimated to include approximately 500 patients in one year.

Publications

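### Two-group comparisons of means rest on Student's t test with no provision for unequal variances; where group sizes and SDs both differ, the 5% level is lost, and Welch's test would hold it

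*Combined protocol and SAP*

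**What the plan says.** The Statistic analysis section sorts continuous variables by distribution. It begins: "Continuous variables will be expressed as mean and standard deviation for those with a normal or Gaussian distribution", and gives the remainder as medians with quartiles. It then states: "The comparison between these variables will be carried out using the Student's t test or the Wilcoxon ranksum test, as appropriate". The error rule is common to every test: "All statistical comparisons will be two-tailed, and p values <0.05 will be considered statistically significant". Welch's test, a variance check and any other rule for unequal spread are absent.

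Three other places bear on group sizes:

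- The fifth objective is to "Compare the clinic, management and evolution characteristics in the different participating Latin American countries".
- Under Participating Centers, the national societies are invited and "they will designate the coronary units where the registry will be carried out". No quota per country is given.
- The Sample line reads: "It is estimated to include approximately 500 patients in one year". No power calculation accompanies it.

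On mortality, the Introduction says of cardiogenic shock that "it is associated with a mortality of 40-50% despite revascularization".

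**The concern.** The pooled t test estimates one common variance, and the larger group dominates that estimate. If the smaller group is the more variable one, the standard error comes out too small and false differences are declared too often. If the smaller group is the less variable one, the standard error comes out too large and real differences are missed.

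Imbalance is plausible here. Country totals depend on which units join and how many shock patients they admit. The Introduction says that ventricular supports see little use in the region, yet Information gathering records ECMO and other supports, so some device groups may be small. The same section lists many separate complications, each of which can define a small group. Unequal spread is also plausible, because SCAI stages C, D and E are taken together and the severity mix may differ between subgroups. The documents establish neither condition as fact.

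What is at stake is whether the stated 5% rule means what it says in those comparisons.

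**Working it through.** **Inputs from the documents.** Two-sided level 0.05 (Statistic analysis); about 500 patients (Sample line); mortality 40-50% (Introduction).

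**Inputs assumed.** Group split 250/250 to 50/450; ratio of SDs, small group over large group, 0.5 to 2; normal data with equal means.

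**The plan's own figure.** The two-sided critical value is z = 1.960, and 2 × (1 − Φ(1.960)) = 0.0500. With equal SDs, the simulated level of Student's test is 4.9-5.0% at every split. The declared level is therefore reproduced when variances are equal, however unequal the groups.

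**Formula.** With n₁ the small group (SD = r) and n₂ the large group (SD = 1):

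- true variance of the difference: T = r²/n₁ + 1/n₂
- variance the pooled test uses: P = [((n₁−1)r² + (n₂−1)) / (n₁+n₂−2)] × (1/n₁ + 1/n₂)
- actual level ≈ 2 × (1 − Φ(1.960 × √(P/T)))

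**50/450, SD 1.5 times larger in the small group.** T = 2.25/50 + 1/450 = 0.04722. P = (559.25/498) × 0.02222 = 0.02496. √(P/T) = 0.727, and 1.960 × 0.727 = 1.425, so the level is 15.4% (simulation 15.5%).

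**50/450, SD 1.5 times smaller in the small group.** T = 0.4444/50 + 1/450 = 0.01111. P = (470.78/498) × 0.02222 = 0.02101. √(P/T) = 1.375, and 1.960 × 1.375 = 2.695, so the level is 0.70% (simulation 0.75%).

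**Range.** Simulated level of Student's test in per cent, 200,000 runs per cell:

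| Split (small/large) | SD ratio 0.5 | 0.67 | 0.8 | 1 | 1.25 | 1.5 | 2 |
|---|---|---|---|---|---|---|---|
| 250/250 | 5.0 | 5.0 | 5.0 | 5.0 | 5.0 | 5.0 | 4.9 |
| 200/300 | 2.8 | 3.5 | 4.0 | 4.9 | 6.1 | 7.0 | 8.2 |
| 150/350 | 1.2 | 2.2 | 3.2 | 5.0 | 7.2 | 9.3 | 12.6 |
| 100/400 | 0.4 | 1.3 | 2.6 | 4.9 | 8.6 | 12.1 | 17.9 |
| 50/450 | 0.08 | 0.75 | 1.9 | 5.0 | 10.0 | 15.5 | 24.6 |

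Welch's test gives 4.9-5.1% in all of these cells.

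A comparison of two countries need not add up to 500. At 300 versus 30 with a 1.5-fold SD difference, Student's test gives 15.6% or 0.7% and Welch's test 5.0%.

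**Deaths versus survivors.** Mortality of 40-50% implies about 200/300 to 250/250. At 200/300 with r = 1.5: T = 0.01458, P = 0.01250, √(P/T) = 0.926, level 7.0%. With the SD ratio reversed it is 3.5%. At 225/275 (45% mortality) the pair is 6.0% and 4.2%.

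**Rank-sum test.** At 50/450 with SD ratio 1.5 or 0.67 it gives about 9% or 2% (4,000 runs). It is affected too, but less.

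**The case against.** The strongest reply is that the harm depends on quantities the plan never gives. There are no patient numbers per country, no device or complication frequencies and no SDs. That stands: every percentage above other than the nominal 5% is conditional on assumed inputs.

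A reader might infer that unequal group sizes alone break the test. They do not, as the column for SD ratio 1 shows. A reader might also take roughly 16% as the registry's error rate. The documents do not support that either. Reaching 16% needs an SD ratio of about 1.53 at 50/450, 1.81 at 100/400 and 3.0 at 150/350, and no ratio reaches it at 200/300.

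A third tempting inference is that the mortality model will be badly contaminated, because univariate significance decides which variables enter it. At the plan's own mortality the two groups are close to balanced, so that screen is only mildly affected.

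It can also be said that the plan never writes the word pooled, and that its closing qualifier leaves room for judgement. Pooling is nevertheless the ordinary meaning of the named test. Since the preceding sentence sorts variables by normality, the qualifier most naturally chooses between the t and rank-sum tests, not between variance assumptions.

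Finally, the Ethical considerations section calls the study descriptive, and no primary hypothesis or power calculation hangs on this test. That limits the weight of the point but does not remove the case for the better test.

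**Conclusion.** The point holds in a limited form. The plan names Student's t test as its only two-group test of means and has no provision for unequal variances, while several of its comparisons involve groups whose sizes are left to chance. If sizes and SDs both differ, the 5% level is not kept. Over the assumed range it runs from about 5% up to about 25%, or down to about 0.1%. A modest 1.25-fold SD difference at 50/450 already gives about 10% or 1.9%.

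The concern applies to country, device and complication comparisons. It has little force for deaths versus survivors, where the level stays at about 3.5% to 7% for a 1.5-fold SD difference. This is a cheap improvement to a descriptive registry, not a defect that undermines its main results.

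**What to change.** In the Statistic analysis section, replace Student's t test with the following: *Two-group comparisons of means use Welch's unequal-variance t test, without a preliminary test of variances; the mean difference is reported with its Welch 95% confidence interval.*

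The cost is one line. If the variances are in fact equal, the loss of power in a very unbalanced comparison is about 2 points: 73.8% for Student against 71.7% for Welch at 300 versus 30 and a true difference of 0.5 SD. Naming the test in advance also removes a choice that could otherwise be made after seeing the data.

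The change does not repair rank-sum comparisons, and it does not supply an overall test if more than two countries are compared. Those need their own wording.

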Patients of both sexes and older than 18 years, admitted to a coronary or polyvalent critical care unit, for an acute coronary syndrome with or without ST-segment elevation who present with cardiogenic shock from admission or develop it during hospitalization and who can be followed up in its evolution until hospital discharge

Exclusion criteria:

Non-ischemic cardiogenic shock (chronic heart failure, myocarditis, sepsis, tachycardiomyopathy, Takotsubo, etc.). Cardiogenic shock A and B of the new SCAI classification.

Information gathering:

The following variables will be analyzed: age, sex, risk factors and comorbidities, previous treatment, characteristics of the AMI that generated the shock, location of the infarction, Killip and Kimball on admission and evolution, time of evolution on admission, reperfusion strategies (fibrinolysis or angioplasty), if angioplasty was required: what type (primary, rescue, delayed), number of vessels operated, drug treatment instituted, hemodynamic monitoring and mechanical support (balloon pump, ECMO, mechanical ventilation, others).

The in-hospital evolution and eventual complications (fever, sepsis, COVID 19, multiorgan failure, arrhythmias, reinfarction, post-infarction angina, mechanical complications, transfusion requirement, major and minor bleeding) will be studied. Laboratory data will be collected upon admission and at 24 hours. Hemodynamic measurements will be recorded at the time of Swan Ganz catheter placement and at 24 hours (if used) and echocardiogram data. The follow-up will only be in-hospital.

The data will be collected by the researchers from the different participating centers through an electronic file developed ad hoc in Red Cap and the data will be analyzed by the executive committee that will be made up of members of the research area of the Argentine Society of Cardiology.

The Red Cap platform is a secure web application for online data management. The data will be stored securely on a server at the Argentine Society of Cardiology. For centers without Internet access, it is possible to collect data offline through Red Cap using the Red Cap mobile application that is downloaded to a tablet or mobile device. With the app, data can be collected offline and then synced with Red Cap's server. While Attachment 1 can also be printed and used to collect data for subsequent electronic submission, direct collection of electronic data is preferable to avoid transcription errors.

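### The plan has no rule for ordered variables. If Killip class on admission and vessel count are tested as discrete, the unordered chi-square loses about 9 to 16 points of power where an ordered test would have 80%.

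*Combined protocol and SAP*

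**What the plan says.** The Statistic analysis section has two test rules.

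- Continuous variables are summarised by mean or median. On testing: "The comparison between these variables will be carried out using the Student's t test or the Wilcoxon ranksum test, as appropriate".
- For the rest: "Discrete variables will be expressed as percentages". On testing: "Statistical comparisons between them will be made using the chi-square test with Yates correction or Fisher's exact test, as appropriate".

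No trend test, Kruskal-Wallis test or ordinal model is named. On significance: "All statistical comparisons will be two-tailed, and p values <0.05 will be considered statistically significant". On building the models: "The variables of univariate statistical significance will be entered for evaluation in the different regression models".

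The Information gathering section lists two kinds of ordered measure: "Killip and Kimball on admission and evolution" and, for patients who needed angioplasty, "number of vessels operated". Neither is assigned to a variable type. The fourth objective concerns predictors of in-hospital mortality, and the fifth compares countries. The Study organization section expects about 500 patients.

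**The concern.** A graded severity class is not a continuous variable with a mean or a Gaussian shape. By exclusion it falls under the discrete rule, where the analyst may choose only between chi-square and Fisher. Both treat the grades as unrelated labels: shuffling the classes would leave the p value unchanged.

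Two things are at stake. First, a real shift in severity on admission, or in the extent of angioplasty, between countries or patient groups would be missed more often than it need be. Second, univariate significance decides what enters the regression models. If the order-blind test is the screen, Killip class on admission could be kept out of the mortality model although risk rises steadily across its classes.

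**Working it through.** **Nothing to reproduce.** The plan states no power, effect size or class distribution. The 500 is a recruitment estimate.

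**Inputs from the documents.** Two-sided alpha 0.05; about 500 patients; mortality of 40-50% (Introduction).

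**Assumptions.** Four Killip classes; three levels of vessel count; the class mixes and odds ratios shown below.

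**Step 1: two groups, analytic.** Power on d degrees of freedom is the probability that a noncentral chi-square with noncentrality λ exceeds the 95% point of the central chi-square. An ordered test puts the signal on 1 df. The unordered test spreads the same λ over (levels − 1) df. The critical values are 3.841, 5.991 and 7.815 for 1, 2 and 3 df. For 80% power on 1 df, λ = (1.960 + 0.842)² = 7.85. The same λ gives 70.9% on 2 df and 64.5% on 3 df.

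| Power of ordered test | Loss, 3 levels (points) | Loss, 4 levels (points) |
|---|---|---|
| 50% | 9.9 | 15.5 |
| 60% | 10.5 | 16.8 |
| 70% | 10.3 | 16.9 |
| 80% | 9.1 | 15.5 |
| 90% | 6.5 | 11.6 |
| 95% | 4.2 | 7.9 |

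**Step 2: two groups, simulated.** Proportional-odds shift with OR 1.65, 250 v 250, Pearson chi-square against tie-corrected rank-sum:

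| Assumed mix | Chi-square | Rank-sum |
|---|---|---|
| Killip I-IV 30/20/10/40% | 72% | 85% |
| Killip I-IV 20/15/10/55% | 65% | 80% |
| Killip I-IV 25% each | 75% | 88% |
| Vessels 60/28/12% | 74% | 83% |

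With no true difference the rank-sum test rejects about 5% of the time.

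The vessels row gives all 500 patients a count, but only angioplasty patients have one. At an assumed 70% angioplasty (500 × 0.70 = 350, so 175 v 175), rank-sum power falls to about 68%. The gap stays near 10 points.

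In a small and unequal comparison with a modest effect (50 v 450, OR 1.3), even the ordered test has little power, and the gap is 3 to 5 points.

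**Step 3: several countries.** The number of countries is not given. If Kruskal-Wallis (groups − 1 df) has 80% power, the unordered chi-square, on (groups − 1) × (levels − 1) df, loses the following for 3 and 4 levels: 10.2 and 17.5 points with 3 groups, 11.8 and 20.2 with 5, and 13.3 and 22.6 with 8.

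**Step 4: death by Killip class, 500 patients.**

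- Steady gradient (37/42/47/52%, mix 30/20/10/40): chi-square 66%, trend test 81%.
- Only class IV differs (40/40/40/52%): the trend test is about 7 to 9 points ahead of the four-class chi-square in the two unequal mixes, and about 3 behind with equal classes. Against a class IV v I-III contrast with Yates correction it is behind in all three mixes: 65% v 72%, 68% v 74% and 44% v 61%.

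**The case against.** **Placement is an inference.** The plan assigns neither variable to a type. An analyst could treat vessel count as a non-Gaussian number and use the rank-sum test already named. This stands, so the point is a missing rule and a conditional loss. Killip class has no such natural route.

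**A two-level cut.** Because Yates correction belongs to 2 × 2 tables, a reader might infer that Killip class will be cut in two, and count further losses from that. The plan states no such cut, so no loss is claimed for it. As Step 4 shows, a cut at class IV would beat the trend test if only class IV differs.

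**Killip class during evolution.** A reader might count it as an equal example. Every patient has shock by the inclusion criteria. If the field records the worst class reached, it may be nearly constant and hold little order to use. Killip on admission does vary, because shock may develop later in the stay.

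**The mortality model.** A reader might infer that Killip class will be dropped. The plan does not say which univariate test is the screen. A univariate logistic model with class entered as a score would use the order.

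**Low consequence.** The Ethical considerations section calls the study descriptive, no primary hypothesis or power target is stated, and frequency tables can show every class whatever the test. The choice of test in itself biases no reported percentage or odds ratio. This stands and limits the point to an optional improvement.

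**Conclusion.** The concern holds in a conditional form. The plan lacks a rule for ordered variables. If Killip class on admission and vessel count go under the discrete rule, their order is ignored. For two groups whose difference follows the order, with ordered power of about 80%, the loss is about 9 points (3 levels) to 16 points (4 levels).

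That range is not a fixed property of this registry. It shrinks when power is very high or very low, and it can be larger across several countries. It rests on assumed level counts, class mixes and a proportional-odds shift, and it does not apply to patterns that are not monotone. The effect on the mortality model is possible, not established. Importance is low and confidence medium.

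**What to change.** Add to the Statistic analysis section:

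*Ordered variables (Killip class on admission; number of vessels treated, in angioplasty patients) will be compared between two groups with the tie-corrected Wilcoxon rank-sum test and between several countries with the Kruskal-Wallis test. Their association with in-hospital death will be tested with a trend test that keeps all classes. The unordered chi-square or Fisher test and the full class distribution will be reported alongside.*

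Also state that the ordered test is the main one, so that the choice is not made after both p values are seen, and say which univariate test screens variables for the regression.

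The cost is one or two sentences plus that clarification. No new data are needed, and the rank-sum test is already in the plan. The downside is that an ordered test has less power when the pattern is not monotone or when only class IV differs. The unordered test and the full distribution are kept for that reason.

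### The mortality regression has no method for missing covariates and no limit on time points, so a default fit may lose patients, and a 24-hour variable would remove every death before 24 hours

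*Combined protocol and SAP*

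**What the plan says.** Objective 4 reads "Evaluates predictors of in-hospital mortality". The Statistic analysis section, which is the whole analysis plan, says the search for independent predictors of the end points "will be carried out by means of linear regression analysis and / or multiple logistic". Covariates are chosen by a screen: "The variables of univariate statistical significance will be entered for evaluation in the different regression models". Each covariate's result "will be expressed as adjusted Odds Ratio and its corresponding 95% confidence interval". In-hospital death is binary and the output is an odds ratio, so logistic regression is the relevant model here. The data are to be "analyzed using the statistical programs Epi-info and / or IBM SPSS".

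Under Consent of the patient, the registry "only requires data that has already been collected and is available in the" medical record. Information gathering lists history, prior treatment, infarct features, echocardiography, laboratory data on admission and at 24 hours, and right-heart catheter measurements where a catheter was used. The Inclusion criteria require that the patient can be followed to discharge, so vital status should be known.

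The plan contains no complete-case statement, no imputation, no sensitivity analysis, no reporting of missingness, and no rule on which measurement times may enter the mortality model.

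**The concern.** A logistic fit needs a value for every entered covariate. Where no method is named, the usual default is to omit any patient with a gap. The number of covariates is not capped, because the univariate screen decides it, so small gaps in many variables can add up.

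One gap is tied to the outcome by design. A patient who dies before 24 hours has no 24-hour laboratory value, and nothing keeps such a variable out of the model. If one passes the screen, the fitted model contains no early deaths at all. The sickest patients plausibly die first, so the loss may depend on severity and death together, which is the condition under which complete-case odds ratios become biased.

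At stake is whether the Objective 4 odds ratios describe the consecutive registry or a subset enriched for survivors, and whether their 95% intervals can be taken at face value.

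**Working it through.** **Inputs from the documents.** The sample: "It is estimated to include approximately 500 patients in one year" (Study organization). This is an enrolment estimate with no power or precision target, so there is no calculated figure to reproduce. Background mortality: "it is associated with a mortality of 40-50% despite revascularization" (Introduction), which gives 500 × 0.40 = 200 to 500 × 0.50 = 250 deaths. I use 45%, or 225 deaths.

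**Assumptions, because the documents give no figure.** Missing rate per variable, number of covariates, share of deaths before 24 hours, and how strongly early death relates to severity.

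**Step 1: ordinary gaps.** With k covariates, each independently missing at rate q, the complete share is (1 − q)^k. For k = 10 and 500 patients:

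| q | (1 − q)^10 | Complete | Lost |
|---|---|---|---|
| 1% | 0.904 | 452 | 48 (10%) |
| 2% | 0.817 | 409 | 91 (18%) |
| 5% | 0.599 | 299 | 201 (40%) |
| 10% | 0.349 | 174 | 326 (65%) |

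At q = 5% the intervals are about 1/√0.599 = 1.29 times wider. With k = 5 and q = 1% only 25 patients are lost (5%).

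**Step 2: one 24-hour covariate enters.** Let e be the share of deaths before 24 hours. Patients lost = 225e, all of them deaths. Analysed mortality = 225(1 − e) / (500 − 225e).
- e = 10%: 22.5 lost; 202.5/477.5 = 42%.
- e = 30%: 67.5 lost; 157.5/432.5 = 36%.
- e = 40%: 90 lost; 135/410 = 33%.

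**Step 3: effect on the severity odds ratio.** Large-sample simulation: one million patients, mortality about 45%, true odds ratio 2.0 per SD of severity, complete-case logistic fit.
- Missing at random (30%), dependent on severity only, or dependent on death only (30% of deaths lost): the odds ratio stays at 2.00.
- 30% of deaths lost as early deaths, with the chance of early death rising with severity: about 1.75 at log-odds 0.5 per SD, falling to about 1.58 at 1.0 per SD.

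**Step 4: admission variables only.** Ten covariates, 3% base missingness, 30% of deaths early and related to severity as in Step 3. Missingness in early deaths is raised to 15% or 30% on three of the ten (for example laboratory or echo items). The odds ratio is about 1.89–1.93 at 15% and 1.77–1.86 at 30%.

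**The case against.** The plan does not say that incomplete patients are dropped. That is inferred from the default behaviour of a standard logistic fit, and the named software does not force it, since SPSS has an imputation module. The registry is prospective, uses a purpose-built electronic form, and collects items routinely recorded in this condition. Many candidates, such as age, sex and infarct location, should seldom be missing. Gaps that cluster in the same patients would leave more complete cases than Step 1 shows. The study is also described as descriptive, and predictors are one of five objectives.

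These points stand as limits on size. They do not supply a method: where the plan is silent, the default applies, and no form design can produce a 24-hour value for a patient who has died.

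A reader might infer that the model will lose a large share of patients, early deaths above all, and that its odds ratios are biased. The documents do not support that as fact. They give no missing rate, no timing of deaths and no final covariate list. Preferential loss of early deaths is certain only if a 24-hour variable enters. Bias needs joint dependence on death and severity. Odds ratios of 1.71 or 1.61, with interval coverage of 84% or 68%, can be produced by simulation, but only by giving early deaths 15% or 30% missingness on all ten covariates. That leaves 0.85^10 = 20% or 0.70^10 = 3% of them in the model. With the raised rate on three variables, 500 patients and early death related to severity at 0.8 per SD, coverage is 93% or 87%.

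**Conclusion.** The concern holds in conditional form. The plan states neither how missing covariates are handled nor which time points may enter the Objective 4 model, and its own variable list includes measurements that early deaths cannot have.

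If complete cases are used and a 24-hour variable enters, every death before 24 hours is lost. Under the assumption that these are 30% of deaths, that means about 68 patients and a severity odds ratio between 2.0 (early death unrelated to severity) and about 1.58 (strongly related). With admission variables only, loss of early deaths and bias remain plausible but smaller: about 1.77–1.93 under the Step 4 assumptions. The overall loss from ordinary gaps could be minor or more than half, and the documents cannot settle which. The point merits a change before analysis; it does not show that the results will be wrong.

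**What to change.** Add one paragraph to Statistic analysis:

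1. Limit the main Objective 4 model to variables known at admission or shock onset.
2. Fit it after multiple imputation by chained equations, with in-hospital death and the candidate admission variables in the imputation model, and combine results by Rubin's rules. Show the complete-case fit, with its number of patients and deaths, as a sensitivity analysis.
3. Do not impute 24-hour values for patients dead before 24 hours, or values that exist only after a procedure. Analyse 24-hour variables only in patients alive at 24 hours.
4. Report missingness by variable and by vital status.

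If the data form does not already do so, code history items as yes, no or not recorded, so that an undocumented item is not counted as absent. The form is not among the documents, so this part is conditional.

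The cost is one paragraph and a few hours of analysis in SPSS's imputation module or free software. The downside is reliance on a missing-at-random assumption given the recorded data, which the complete-case fit beside it lets readers judge. Other principled methods could serve; what matters is that one is fixed in advance.
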